10.4 Efficacy Endpoints

10.4.1 SF 36

Health related QOL will be assessed by subjects themselves using SF-36 v2 Japanese version. SF-36 assessment is performed before any other procedures and evaluations. Assessment date and results will be recorded in the CRF.

10.5 Laboratory Tests

10.5.1 Hematology

The following laboratory tests will be measured in the laboratory in each study institution. The standard range of each parameter, blood sample collection date and time, and test results will be recorded on the CRF. As a general rule, the laboratory parameters should be measured by the same devices for the same subject throughout the study period.

Platelet count, red blood cell count, white blood cell count, hemoglobin, hematocrit, differential white blood count (neutrophils, eosinophils, basophils, lymphocytes, and monocytes), neutrophil count, eosinophil count, basophil count, lymphocyte count, monocyte count, reticulocyte ratio, MCHC, MCH, and MCV

10.5.2 Serum chemistry

The following laboratory test parameters will be measured in the designated central laboratory. The presence or absence of sample collection will be recorded on the CRF. When additional laboratory tests are performed at the laboratory in the study institution, the standard range, blood sample collection date and time, and tests results will be recorded on the CRF.

Sodium, potassium, chlorine, calcium, phosphorus, BUN, creatinine*, A/G ratio, blood glucose, total protein, albumin, ALT, AST, alkaline phosphatase (ALP), lactate dehydrogenase (LDH), γ-glutamyltransferase (γ-GTP), total bilirubin, direct bilirubin, and indirect bilirubin

*The eGFR will be calculated using the following formula. Age at the date of informed consent should be used for calculation. For male, eGFR (mL/min/1.73 m²) = $194 \times \text{serum creatinine}^{-1.094} \times \text{Age}^{-0.287}$ For female, eGFR (mL/min/1.73 m²) = $194 \times \text{serum creatinine}^{-1.094} \times \text{Age}^{-0.287} \times 0.739$

10.5.3 Urinalysis

The following laboratory test parameters will be measured in the designated central laboratory. The presence or absence of sample collection will be recorded on the CRF.

Glucose, ketone bodies, occult blood, proteins, nitrites, bilirubin, specific gravity, pH, urobilinogen, and white blood cells

10.5.4 D-dimer

A D-dimer assay will be performed at the designated central laboratory for subjects with a history of venous thromboembolism > 6 months before Screening A. D-dimer assay should be performed only after resolution of the venous thromboembolism and after all anticoagulants have been discontinued for at least 30 days. The presence or absence of sample collection will be recorded on the CRF.

10.5.5 PT-INR/APTT

PT-INR/APTT will be measured at the designated central laboratory. The presence or absence of sample collection will be recorded on the CRF.

10.6 Immunoglobulin Test

Serum immunoglobulin levels (immunoglobulins M, G, and A) will be measured in the designated central laboratory. The presence or absence of sample collection will be recorded on the CRF.

10.7 Immunological Test

The following immunology test items will be measured in the designated central laboratory. The presence or absence of sample collection will be recorded on the CRF.

HIV antigen, HIV antibody, HBs antigen, HBs antibody, HBV DNA assay, HBc antibody, HCV RNA assay

10.8 Eastern Cooperative Oncology Group (ECOG) Performance Status

The investigator will evaluate the condition of subjects using the ECOG Performance Status Japanese translation (see Appendix 1). Assessment date and results will be recorded in the CRF.

10.9 Vital Signs

Systolic and diastolic blood pressure, pulse rate, and body temperature (axillary) are measured after the subject rests (approximately for 3 minutes) in the sitting position. The measurement date, time, and results of systolic and diastolic blood pressure will be recorded on the CRF. The measurement date and results of pulse rate and body temperature (axillary) will be recorded on the CRF. If the initial blood pressure on each specified visit is > 130 mmHg systolic or > 80 mmHg diastolic, the blood pressure should be taken 2 additional times at least 5 minutes apart, and date, time and results for all 3 measurements will be recorded on the CRF. When the systolic and diastolic blood pressure is measured 3 times, the mean value of the 3 measurements will be used to make a decision for "5.2 Exclusion Criteria," "8.3.1 Transition criteria to Period II for subjects who withdraw from ," and "8.6.2.2 Dose adjustment due to adverse events." As a general rule, the laboratory parameters should be measured by the same devices for the same subject throughout the study period.

10.10 Height and Weight

Height and weight will be measured. The measurement date and results will be recorded on the CRF.

10.11 12-lead ECG

Twelve-lead ECG will be measured after subject rests (approximately for 5 minutes) in the supine position, and the measurement date and investigator's assessment will be recorded on the CRF. As a general rule, the 12-lead ECG should be measured by the same devices for the same subject throughout the study period. In principle, the 12-lead ECG is taken before the wital

same subject throughout the study period. In principle, the 12-lead ECG is taken before the vital signs, laboratory tests, immunoglobulin test, immunological test, pregnancy test (women of childbearing potential only), and pharmacokinetics.

10.12 Pregnancy Test

Pregnancy test (serum human chorionic gonadotropin [HCG]) will be performed in women of childbearing potential (women who have not had their uteri or bilateral ovaries removed and had their last menstrual within 1 year) in the designated central laboratory. The presence or absence of sampling and pregnancy will be recorded in the CRF.

10.13 ITP Bleeding Score

The investigator will evaluate the bleeding score of subjects using the ITP Bleeding Scale (see Appendix 2). In principle, the same investigator should evaluate the same subjects. Assessment date and results will be recorded in the CRF.

10.14 Pharmacokinetics

The plasma concentration of R406 (active substance) will be measured. Plasma R406 concentrations will be measured by the liquid chromatography-tandem mass spectrometer (LC-MS/MS) method in the designated pharmacokinetic measurement laboratory (the detailed procedure of pharmacokinetic measurement is specified in the separate pharmacokinetic protocol). The date and time of the administration of the study drug from 2 days before to the day of blood sampling for the pharmacokinetic examination and the date and time of blood sampling on the day of the pharmacokinetic examination will be recorded in the CRF.

10.15 Adverse Events

An adverse event is defined as any untoward or unintended sign, symptom, aggravation of a complication, or disease that occurs in a subject, irrespective of the causal relationship with the study drug. The worsening of an efficacy variable is not considered to be an adverse event.

10.15.1 Collection of adverse events

The following information on each adverse event will be recorded in the CRF: name of the adverse event, date of onset, date of resolution (when the outcome is recovered/resolved, recovered/resolved with sequelae, or death), severity, dose at onset, seriousness assessment, action taken on the study drug, other actions taken, outcome, and causal relationship with the study drug. For adverse events that occur from the collection of informed consent to before the start of study treatment, the name of the adverse event and seriousness assessment will be recorded in the CRF.

10.15.1.1 Adverse event collection period

AEs will be collected from the collection of informed consent to the end of the follow-up period

or market authorization.

10.15.1.2 Inquiry about adverse events

The investigator should give sufficient consideration not to affect the voluntary reporting by subjects when conducting interviews with subjects. Specifically, the investigator should ask a general question, such as "Has anything happened since the last visit?"

10.15.1.3 Considerations for recording adverse events

- 1) When a diagnosis is determined from the signs and/or symptoms, the diagnosis will be recorded as an adverse event. Abnormal laboratory test values, abnormal findings, and symptoms associated with the adverse event will not be considered as an adverse event.
- 2) When a diagnosis is not determined from signs and/or symptoms, abnormal laboratory test values, abnormal findings, and symptoms will be handled as adverse events.
- 3) Abnormal laboratory test values and abnormal findings will be handled as an adverse event when they are clinically relevant variations or changes, as judged by the investigator. A clinically relevant variation or change is defined as a variation or change that requires medical intervention or treatment or is out of the normal physiological variation for the subject, as judged by the investigator.
- 4) Abnormal laboratory test values or abnormal findings observed at the start of the screening period should not be handled as an adverse event.
- 5) Diseases, symptoms, and findings present before the informed consent should not be handled as an adverse event.
- 6) Any worsening of a complication, existing symptom, or finding should be handled as an adverse event. Worsening of a complication, existing symptom, or finding is defined as an increase in the frequency or severity of a seasonal or intermittent symptom or finding when the investigator considers that the relevant disease, symptom, or finding before study participation has worsened more than expected.
- 7) Any adverse event that occurs from the collection of informed consent to before the start of the study treatment and worsens after the start of the study treatment is considered as a new adverse event.
- 8) Any surgery or procedure scheduled before the collection of informed consent is not handled as an adverse event.
- 9) Elective surgeries or procedures that have no impact on disease (eg, dental implant surgery, cosmetic surgery, or suture removal after skin suture at the subject's request) are not handled as an adverse event. However, any clinically relevant finding or symptom caused by such a surgery/procedure should be handled as an adverse event.
- 10) Events considered as a worsening within the range expected for the target disease are not handled as an adverse event.

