1.1 Idiopathic Thrombocytopenic Purpura

ITP is an autoimmune disorder characterized by the development of antibodies to platelet membrane proteins and binding of them to platelets or megakaryocyte, which enhances platelet destruction in reticuloendothelial cells in the spleen and suppresses platelet production in bone marrow, thereby causing thrombocytopenia. Although patients with ITP develop thrombocytopenia, they often have normal or increased numbers of megakaryocytes, which are the precursors cells of platelets in the bone marrow. Therefore, ITP is thought to be the main condition in which thrombocytopenia results from increased destruction of platelets rather than inhibition of platelet production, but the etiology of ITP remains unknown and the mechanism of antibody production has not been determined.

The clinical symptom of ITP show various hemorrhagic manifestations on the skin and mucous membrane mainly as the purpura. A platelet count of $<10000/\mu L$ is associated with an increased risk of serious bleeding episodes. Severe mucosal bleeding may be fatal because it may lead to gastrointestinal bleeding or intracranial hemorrhage. In Japan, ITP has been specified as a designated intractable disease by the "Act on Medical Care for Patients with Intractable Diseases" (Act No. 50, 2014). The health administration report from the Ministry of Health, Labour and Welfare in 2017 showed that there were 17618 patients who had a certificate for receiving specific medical expenses (for the designated intractable disease). The annual incidence of newly diagnosed patients in Japan was reported to be 2.4 per 100000 people.

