10.15.4 Serious adverse events

Any adverse event that meets any of the following criteria will be handled as a serious adverse event for all adverse events, including those that occur from the collection of informed consent to before the start of the study treatment. If any serious adverse event occurs, its symptom or laboratory test parameter and the reason for judging it as serious will be recorded in the CRF.

- 1) Death
- 2) Life Threatening
- 3) Initial or Prolonged Hospitalization
- 4) Persistent or Significant Disability/Incapacity
- 5) Congenital Anomaly or Birth Defect
- 6) Other Medically Important Event

Other Medically Important Event is defined as cases that do not immediately threaten life or lead to hospitalization, but may expose patients to danger, or cases associated with medical events that require treatment or procedure to prevent the outcomes listed in the above 1) to 5).

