10.15.5 Adverse events of special interest

The following adverse events are considered as an adverse event of special interest (regardless of seriousness). The details of adverse events of special interest are specified in the Statistical Analysis Plan.

- 1) Bleeding-related adverse events
- 2) Gastrointestinal disorders
- 3) Infection
- 4) Hypertension

- 5) Neutropenia
- 6) Hepatic dysfunction
- 7) Thrombosis, embolism, and thromboembolism

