14.6.2 ITP Bleeding Score

1) Summary statistics will be presented for the mean and total scores of the anatomical sites (9 sites except Skin [Hx] and Oral [Hx]) and distribution of the maximum score will be presented.

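### The exemption for expected worsening of ITP lets bleeds, including serious ones, go unrecorded as adverse events at the investigator's judgement

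*Protocol*

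**What the plan says.** Protocol section 10.15.1.3 lists what is and is not recorded as an adverse event. Item 10) reads: "Events considered as a worsening within the range expected for the target disease are not handled as an adverse event". Item 6) makes worsening of an existing symptom or finding an adverse event only "when the investigator considers that the relevant disease, symptom, or finding before study participation has worsened more than expected". Neither item defines the expected range or excepts any kind of event.

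Three other parts of the protocol bear on how this works for bleeding:

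- **Section 1.1** describes the disease by its bleeding: "The clinical symptom of ITP show various hemorrhagic manifestations on the skin and mucous membrane mainly as the purpura". It adds: "Severe mucosal bleeding may be fatal because it may lead to gastrointestinal bleeding or intracranial hemorrhage".
- **Section 10.15.4** defines seriousness within adverse events: "Any adverse event that meets any of the following criteria will be handled as a serious adverse event".
- **Section 10.15.5** puts "Bleeding-related adverse events" first in the list of events of special interest, whether or not they are serious. SAP Table 5.3-1 gives them a category with eight preferred terms.

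Bleeding is also scored on the ITP Bleeding Scale (sections 10.13 and 14.6.2, Appendix 2), which section 4.2.1 names as a safety endpoint.

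**The concern.** In ITP, bleeding is what expected worsening looks like. Two investigators who see the same new nosebleed or mouth bleed can both follow the protocol, and one will record an adverse event while the other will not. The same wording applies, with no stated limit, to a bleed that meets a seriousness criterion.

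At stake are the special-interest bleeding tables, the causality and follow-up records, and the prompt notice of serious events. The exposure may be greatest after Period I. Section 14.6 limits the planned safety analysis of the Non-dosing period and Period III to adverse events and the Bleeding Score. The SAP later adds other measures there, but none that captures bleeding. A bleed after R788 is interrupted is easily put down to the underlying disease.

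**Working it through.** The plan states no bleeding rate or event count that could be reproduced, so the main check is to follow one bleed through the rules.

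1. A subject bleeds during the study. The general definition in section 10.15 has its own exclusion: "The worsening of an efficacy variable is not considered to be an adverse event". This does not apply, because bleeding is a safety endpoint (section 4.2.1).
2. If the subject had similar bleeding before the study, item 6) asks whether it is worse than expected. In any case, item 10) asks whether it is worsening within the range expected for the disease. Both are left to judgement.
3. Item 10) takes the disease as its standard. Section 1.1 names gastrointestinal and intracranial hemorrhage as part of the possible course, so the wording sets no upper limit of severity.
4. If the bleed is judged expected, it is not an adverse event. Section 10.15.4 then has nothing to classify as serious. Section 10.15.5 has nothing to flag, and sections 10.15.8 (causality) and 10.15.9 (follow-up) do not apply. The 24-hour notice in section 12.2.2 is not triggered.
5. Sections 10.15.1.3, 10.15.4 and 10.15.5 do not refer to one another on this point, so nothing says which prevails.

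**Other records of bleeding.** The Bleeding Score is taken every 2 weeks in Period I, every 4 weeks in Period II and every 8 weeks in Period III. It has no seriousness or causality assessment and no expedited route. Its summary scores use nine sites and leave out the two history items for skin and mouth (Protocol 14.6.2, SAP 5.7). Those items are still collected in the CRF. Rescue therapy is recorded with its reason for use (section 10.3.2), but that covers only bleeds that were treated.

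**Scale, as an illustration only.** The inputs are the overseas rates in section 8.6.3, which are 5/101 (R788) and 5/49 (placebo) for serious bleeding and 10/101 and 8/49 for moderate to severe bleeding. The group sizes are 16 and 8 (section 8.9.1). The share f of bleeds judged expected and not recorded is my assumption; the documents give no value, so it runs from 0 to 1.

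- Expected subjects recorded = (1 − f) × (16 × p_R788 + 8 × p_placebo)
- Chance that neither group has one recorded = (1 − (1 − f) × p_R788)^16 × (1 − (1 − f) × p_placebo)^8

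With f = 0, serious bleeding gives 16 × 5/101 = 0.79 and 8 × 5/49 = 0.82, in total 1.6. The chance of none is 0.444 × 0.423 = 0.188. Moderate to severe bleeding gives 1.58 + 1.31 = 2.9.

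| f (assumed) | Serious: expected recorded | Serious: chance of none | Moderate to severe: expected recorded | Moderate to severe: chance of none |
|---|---|---|---|---|
| 0 | 1.6 | 19% | 2.9 | 5% |
| 0.25 | 1.2 | 29% | 2.2 | 10% |
| 0.5 | 0.8 | 44% | 1.4 | 22% |
| 0.75 | 0.4 | 67% | 0.7 | 48% |
| 1 | 0 | 100% | 0 | 100% |

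Section 1.4.1 uses denominators of 102 and 48. With 5/102 and 5/48 the serious total is again 1.6 and the chance of none is again 19%.

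**The case against.** The strongest reply is that a reader might infer that item 10) takes bleeding out of adverse event reporting altogether, and the documents do not support that. The item exempts only worsening judged to be within the expected range. SAP Table 5.3-1 lists eight bleeding terms, several of them ordinary signs of ITP, while the thrombosis row is marked not applicable. SAP section 16.3 says the terms were changed to add applicable events at the second cutoff. The list therefore appears to follow events that were coded, which means that bleeding was being recorded. This stands. It does not show that recording was complete or that sites used one standard.

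Other points in the plan's favour:

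- **Serious bleeds.** Exclusion criterion 9) keeps out patients with a Grade 2 score at any site, so a life-threatening bleed would be hard to call expected. This makes the omission less likely, but the wording still allows it.
- **Blinding.** Investigators are blinded in Period I, so the judgement should not systematically favour one group. This stands for the comparison. It does not help the completeness of safety reporting, and it does not apply to the open-label periods.
- **Bleeds between visits.** One might infer that skin and mouth bleeds between visits are lost. They are not: the history items are in the CRF and are only left out of the summary scores.
- **Overseas rates.** One might infer that the bleeding rates cannot be compared with the overseas studies. The recording rules of those studies are not in the documents, so comparability is unverified rather than disproved.
- **Weight of one event.** One unrecorded subject is most of the expected total only for serious bleeding (1 of 1.6). For moderate to severe bleeding it is about a third (1 of 2.9). SAP section 6.5.2 treats everything except the primary endpoint as for reference only, so no formal test is affected.

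**Conclusion.** The point holds as a conflict between recording rules. Followed as written, items 6) and 10) permit a bleed, including a serious one, to stay out of the adverse event, special-interest, serious-event and 24-hour routes on an undefined judgement. The Bleeding Score and the rescue records are only a partial substitute.

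The extent of any under-recording cannot be determined from the documents. The table above rests on two assumptions: that the overseas rates apply to Period I of this trial, and that f takes the values shown. It shows how few judgements would alter the bleeding tables at this sample size, and nothing about what happened. The primary endpoint is not affected. The change is worth making because it protects safety reporting at little cost.

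**What to change.** Reconcile sections 10.15.1.3, 10.15.4 and 10.15.5 by adding to both item 6) and item 10) that the exemption for expected worsening does not apply to:

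- (a) any event that meets a seriousness criterion in section 10.15.4; or
- (b) any bleeding event in the special-interest category of section 10.15.5 that is worse than the Day 1 ITP Bleeding Score grade at that site, or that leads to rescue therapy.

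These events are recorded as adverse events and assessed for seriousness and causality. Both items need the text, since changing item 10) alone would leave item 6) in conflict with it. Tying (b) to a rise in grade or to rescue avoids recording every new bruise. The category should be the protocol's, because the SAP term list appears to follow events already coded.

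For data already collected, compare rises in the Bleeding Score from Day 1 and all rescue records with the adverse event and serious adverse event listings. Use all the scored sites, including the two history items. Report any bleed that was left out under item 6) or 10), by period and treatment group.

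The cost is protocol wording, one reconciliation listing, some additional adverse event records and slightly higher bleeding counts. The change concerns recording only and alters no treatment.

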10.15.2 Onset date of adverse events

- Date when the subject or investigator noticed the sign or symptom
- Date when the subject or investigator noticed the aggravation of the complication, existing

symptom, or finding

- Date of diagnosis confirmed even if the time of onset can be estimated for asymptomatic diseases
- For abnormal laboratory test values and abnormal findings, the date of examination from which a clinically relevant variation or change is obtained, as judged by the investigator

10.15.3 Severity of adverse events

The severity of adverse events will be evaluated with a 3-rank scale according to Table 10.15.3-1. The most severe rank will be recorded for adverse events that vary in severity.

Table 10.15.3-1 Severity of Adverse Events

Severity	Decision criteria
Mild	Events that do not interfere with activities of daily living, ^{a)} or slightly interfere with them but
	do not require particular treatment, or require simple treatment
Moderate	Events that interfere with activities of daily living ^{a)} and require treatment
Severe	Events that make activities of daily living ^{a)} almost impossible or requiring systemic treatment

a) For example, sleeping, moving, working, going out, eating, exercise, and bathing

